## SYNOPSIS

Name of Sponsor/ Company: Bausch & Lomb Incorporated
Study: #916
Name of Investigational Product: Bausch + Lomb (kalifilcon A) Daily Disposable Multifocal Contact Lens
Title of Study: A Study to Evaluate the Product Performance of a New Silicone Hydrogel Multifocal Contact Lens
Number of Clinical Centers: Approximately 18 to 20 investigative sites in the United States
Objective: The objective of this study is to evaluate the product performance of a new silicone hydrogel daily disposable multifocal contact lens, the Bausch + Lomb (kalifilcon A) Daily Disposable Multifocal Contact Lens, when worn by current soft contact lens wearers on a daily disposable wear basis.
Methodology: This is a single-treatment study evaluating the product performance of a new silicone hydrogel multifocal daily disposable contact lens.

 
• Approximately 300 subjects (600 eyes) will be enrolled in this 3-week, single-arm, bilateral, open-label study at approximately 20 investigative sites in the United States.
 
• Habitual wearers of multifocal soft contact lenses will be required to wear dispensed study lenses on a daily disposable basis for approximately 3 weeks, with scheduled in-office follow-up visits at 1 week and 3 weeks
 

Number of Subjects Planned: Approximately 300 subjects (600 eyes), with at least 270 subjects expected to complete the study.

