## **3.0 STUDY DESIGN**

### **3.1 Description of Study Design**

The is a single-treatment study evaluating the product performance of a new silicone hydrogel multifocal daily disposable contact lens.

Approximately 300 subjects (600 eyes) will be enrolled in this 3-week, single-arm, bilateral, open-label study at approximately 20 investigative sites in the United States.

The study is designed to include habitual wearers of multifocal lenses. All subjects will be seen for a Screening/Dispensing Visit, at which time informed consent will be obtained and eligibility will be assessed.

All consented subjects will be assigned a subject identification (ID) number in sequential order by the Electronic Data Capture (EDC) system. At the Screening/Dispensing Visit, all eligible subjects will receive study contact lenses to wear on a daily disposable basis for approximately 3 weeks, with scheduled in-office follow-up visits at 1 week and 3 weeks.

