### **3.3 Selection of Study Population**

Recruitment for the study may start at any point after the Investigator agrees, in writing, to participate in the study. Written informed consent, including Health Insurance Portability and Accountability Act (HIPAA), enrollment in the study, or dispensing of study products cannot begin until the Investigator has received Institutional Review Board (IRB) and Sponsor approval to conduct the study. The Sponsor and IRB must approve any advertising used to recruit subjects prior to use of that advertising.

All consented subjects must be accounted for, whether or not they participate in the study. The Sponsor will record information for each potential study subject who signs an ICF.

Once a potential subject is consented, their information will be recorded on the screening log and the Investigator should proceed with screening procedures.

Potential subjects will be classified as eligible or “Screen Failures.” A subject deemed a Screen Failure cannot participate in the study since he/she has not met the study inclusion criteria or has met the exclusion criteria. Electronic case report forms (eCRFs) must be completed for screen failure subjects and a copy of their signed ICF, and any information collected as part of screening (e.g., source documents, etc.) must be kept in their permanent records.

Once a subject is enrolled (i.e., a subject ID number is assigned), a subject is considered active and must be accounted for at every visit until exited (completed or discontinued) from the study, even if they are not dispensed study materials. Refer to [Section 3.3.4](#) for subjects determined to be lost to follow-up.

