#### **3.3.1.2 Exclusion Criteria**

1. Subjects participating in any drug or device clinical investigation within 30 days prior to entry into this study and/or plan to do so during the period of study participation
2. Subjects who are women of childbearing potential (those who are not surgically sterilized or postmenopausal) are excluded from participation in the investigation if they meet any one of the following conditions:
  - She is currently pregnant

- She plans to become pregnant during the study
- She is breastfeeding

3. Subjects with any systemic disease currently affecting ocular health or that, in the Investigator's opinion, may have an effect on ocular health during the course of the study
4. Subjects with an active ocular disease
5. Subjects who have had any corneal surgery (e.g., refractive surgery)
6. Subjects who have worn gas-permeable (GP) contact lenses within the last 30 days or who have worn polymethylmethacrylate (PMMA) lenses within the last 3 months
7. Subjects who currently wear monovision or toric contact lenses
8. Subjects who are not correctable to 32 letters (0.3 logMAR) with bilateral soft multifocal contact lenses
9. Subjects with an ocular astigmatism >1.00 D in either eye
10. Subjects with anisometropia (spherical equivalent) >2.00 D
11. Subjects with any Grade  $\geq 2$  finding during the slit lamp examination. Subjects with corneal infiltrates of ANY GRADE are not eligible
12. Any "Present" finding during the slit lamp examination that, in the Investigator's opinion, interferes with contact lens wear
13. Any scar or neovascularization within the central 6 mm of the cornea. Subjects with minor peripheral corneal scarring (that does not extend into the central area) that, in the Investigator's opinion, does not interfere with contact lens wear are eligible for this study
14. Subjects who are amblyopic
15. Subjects using any systemic or topical ocular medication that will, in the Investigator's opinion, affect ocular physiology or lens performance
16. Subjects who are allergic to any component in the study care products

If a subject meets all the inclusion criteria and does not exhibit any of the exclusion criteria, the subject is eligible for entry into the study. Ineligible subjects MUST NOT be enrolled in this study. Any subject enrolled in the study who later is found to have not met the eligibility criteria at entry will be discontinued.

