### **3.3.3 Subject Discontinuation**

A subject MAY be discontinued (at the discretion of the Investigator, the Sponsor, and/or the IRB) prior to the final study visit for a variety of reasons, including, but not limited to:

- An AE occurring during the course of the study, which precludes continued treatment or follow-up

- Persistent Grade 3 or 4 slit lamp findings
- Persistent study-related symptoms/complaints
- Unacceptable contact lens visual acuity (VA)
- Unacceptable contact lens centration
- Unacceptable contact lens movement
- Failure to follow study procedures

A subject MUST be discontinued prior to the final study visit for any of the following reasons:

- Voluntary withdrawal
- Death
- Investigator decision that it is not in the best medical interest of the subject to continue participation in the investigation
- Lost to follow-up ([Section 3.3.4](#))
- Either eye is discontinued
- Becomes pregnant during the study

Prior to discontinuing a subject, every effort should be made to contact the subject, schedule a final study visit, obtain as much follow-up data as possible, and retrieve all study materials. Adverse events will be followed as described in [Section 6.0](#).

Subject discontinuations must be documented clearly on the source document and applicable eCRF. The Investigator should indicate the PRIMARY (one) reason that the subject was discontinued for each eye. Subjects who voluntarily withdraw from the study are not required to provide a reason for their decision but should be encouraged to share this information. Subjects who are discontinued from the study following enrollment will not be replaced.

Exit Visit assessments should be completed for early discontinued subjects, if possible.

At the final study visit, all study subjects who are discontinuing should be examined to ensure that their ocular health is consistent with pre-study, baseline conditions. Any adverse effects determined to have been reasonably caused by participation in the study will be followed per the standard of care. Participation in the study will not impact post-study choices of study subjects for correcting their vision using marketed products (e.g., contact lenses and contact lens care solutions).

Whether a subject completes or is discontinued from the study, they will be directed by the Investigator to resume their habitual method of vision correction.

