i. Perform a slit lamp examination. Record all slit lamp findings and at a minimum sketch the following in the subject's source document:

- Any ungraded finding marked as “PRESENT”
- Any corneal scars
- Any corneal staining
- Any corneal infiltrate
- Any other graded slit lamp findings Grade >2

j. Assess eligibility. Indicate on the Screening Log whether the subject is a “Screen Pass” or “Screen Fail.” “Screen Fail” subjects are ineligible and cannot be enrolled in the study. The reason for screen failure must be documented on the Screening Log and in the subject record and maintained with a copy of their ICF.

k. Administer the Baseline Questionnaire.

l. Dispense 10 study contact lenses per eye according to the Fitting Guide and dispense all study materials.

- **The subject MUST insert the study lenses at this visit.**

*Note: Study lenses should be allowed to equilibrate a minimum of 10 minutes on the eye. Subjects should be encouraged to walk around, read, and/or look outside while the lens is equilibrating. If the vision is unsatisfactory, the lenses should be refined by adding add power according to the fitting guide to achieve acceptable vision. Number of refinements completed to achieve satisfactory vision in each eye will need to be collected.*

- Order remaining study contact lenses on Stock Material Order Form.

m. For the dispensed lenses, perform the following assessments:

- Dispensed lens sphere power
- Dispensed lens add power (high, low, or none)
- Distance (OU), intermediate (OU), and near (OU) lens VA
- Lens wettability
- Lens centration
- Lens movement

n. Compare the high-contrast OU distance lens VA to the high-contrast OU distance BSCVA obtained at this visit. If the VA has decreased by  $\geq 10$  letters, explain.

- o. Have the subject complete the abbreviated Lens Performance Rating Scales for study lenses using the 0-100 rating scales provided by the Sponsor.
- p. Collect/assess all AEs/ADEs, including serious or significant non-serious AEs.
- q. Provide instructions for study contact lens wear to the subject and instruct the subject to wear their study lenses to the 1-Week Follow-Up Visit.
- r. Register subject information in ePRO system **while subject is in office**. This should be done only for eligible, dispensed subjects. Subject data to be entered for registration:
  - Subject number
  - Date of birth
  - Subject phone number (text capability)
  - Screen date

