### **7.8.2 Sample Size Determination**

Approximately 300 subjects will be enrolled. Allowing for up to 10% losses, power calculations were completed for 270 completed subjects. An exact binomial test with a nominal 5% one-sided significance level will have 93% power to detect the difference between the Null hypothesis proportion,  $\pi_0$  of 0.5 and the Alternative proportion,  $\pi_1$ , of 0.6 when the sample size is 270.

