6.5.3 Disposition of Subjects

Disposition summaries will be presented for all enrolled subjects. These summaries will include an accountability of subjects, summarizing the number and percentage of subjects in the following categories: active subjects, eligible at the Screening Visit, and ineligible at the Screening Visit. A subject is considered active once enrolled until completing or discontinuing from the study. In addition, within the eligible and ineligible at baseline categories, the number and percentage of subjects who have completed the study and discontinued the study will be presented. Lens dispensation status will be presented for discontinued subjects. All percentages will be based on the number of subjects enrolled, except that dispensation status percentages will be based on the number of discontinued subjects. Subject status will also be summarized by investigational site.

Subjects and eyes in the Full Analysis Set and the Safety Analysis Set will be summarized as well, with percentages based on all enrolled subjects/eyes.

The reasons for study discontinuation will also be summarized for each eye. Only the primary reason for study discontinuation will be recorded. Percentages will be based on the number of eyes for all enrolled subjects.

Details of discontinued eyes and ineligible subjects will be presented separately. Subject listings will also be provided for disposition data, as well as analysis sets and inclusion/exclusion criteria.

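### Does the double use of 'enrolled' (ID assigned at consent, or eligibility passed) leave the target of 300 and the disposition tables undefined?

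*Protocol*

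**What the plan says.** Two uses of the word appear in the documents.

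- **By ID.** Protocol 3.1, repeated in SAP 4: "All consented subjects will be assigned a subject identification (ID) number in sequential order". Protocol 3.3 then ties enrolment to that event: "Once a subject is enrolled (i.e., a subject ID number is assigned), a subject is considered active". The sentence goes on to require that such people be accounted for until they exit, whether or not they received lenses. SAP 6.5.3 uses the word this way: its disposition summary covers all enrolled subjects and has the categories "active subjects, eligible at the Screening Visit, and ineligible at the Screening Visit".
- **By eligibility.** Protocol 3.3.1.2, repeated in SAP 6.2: "Ineligible subjects MUST NOT be enrolled in this study". Step j of Protocol 5.1.1 says of anyone logged as a screen failure that such "subjects are ineligible and cannot be enrolled in the study".

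Three provisions then use the word or depend on it. Protocol 7.8.2 sets the target: "Approximately 300 subjects will be enrolled". The Synopsis adds "with at least 270 subjects expected to complete the study". Protocol 3.3.3 rules out making good the losses: "Subjects who are discontinued from the study following enrollment will not be replaced".

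**The concern.** The ID is issued at consent, before eligibility is checked. Under the definition in Protocol 3.3, each screen failure is therefore already enrolled and breaches the prohibition in 3.3.1.2.

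A strict reader can go further. A screen failure would be someone enrolled, found ineligible, discontinued and not replaceable. Screen failures would then use up places among the 300, recruitment could stop at 300 consents rather than 300 fitted subjects, and the 270 completers behind the power statement might not be reached. The discontinuation percentages in the disposition table would also mix people who left the study with people who never received a lens.

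**Working it through.** **1. The plan's own figure.** Inputs from Protocol 7.8.2: null 0.5, alternative 0.6, one-sided 5%, n = 270. The smallest count c with P(X ≥ c | 270, 0.5) ≤ 0.05 is 150, with exact size 0.0387. Power is P(X ≥ 150 | 270, 0.6) = 93.9%, which agrees with the stated 93%. The enrolment figure is 270 / 0.90 = 300, so one 10% loss allowance accounts for the whole gap and nothing is set aside for screen failure.

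**2. What the context says about the 300.**

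| Place | Content | Points to |
|---|---|---|
| Protocol 3.3 (definition), 3.1 | an ID means enrolled, and IDs are given at consent | all consented |
| Protocol 5.1.1, step j | screen failures are not enrolled | eligible |
| Protocol 5.2.2 with 5.1.1, step r | each enrolled subject gets the survey address; survey registration is for eligible, dispensed subjects only | eligible and dispensed |
| Protocol 7.8.2 | 300 to 270 by a single loss allowance | eligible |
| Protocol 5.1.1, opening | the log of consented people is closed when it is full or when the investigator's quota is met | quota is not simply a count of consents |

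The definition in 3.3 stands in a paragraph about accounting for everyone who signed a consent form. It works as a tracking rule. The provisions that govern recruitment and the survey use the narrower meaning.

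**3. Does the no-replacement rule reach screen failures?** The discontinuation sentence in Protocol 3.3.1.2 concerns people who are later found not to have met the criteria at entry, which naturally means an error discovered after entry. Protocol 3.3 gives screening failures their own class. The Exit Form in 5.1.4 lists non-dispensed as a status separate from discontinued. Neither list of reasons in 3.3.3 names screen failure, although the first list is not exhaustive. The rule bars replacement of discontinued subjects, so a person never dispensed need not fall under it. Protocol 3.4 also lets the sponsor raise enrolment at active sites or add sites.

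**4. The adverse reading, for size.** Assume that the 300 counts IDs, that screen failures are not made good, and that 10% of dispensed subjects are lost. The documents give no screen-failure rate s, so a range is shown. Dispensed = 300(1 − s); completers = 0.9 × dispensed. Power is for the same exact test with every completer giving an agree or disagree answer.

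| s (assumed) | Dispensed | Completers | Critical count | Power at 0.6 |
|---|---|---|---|---|
| 0% | 300 | 270 | 150 | 93.9% |
| 5% | 285 | 256 | 142 | 93.8% |
| 10% | 270 | 243 | 135 | 93.0% |
| 20% | 240 | 216 | 121 | 89.6% |
| 30% | 210 | 189 | 107 | 84.7% |

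On this reading 270 completers would need a loss among dispensed subjects of no more than 1 − 270/285 = 5.3% at s = 5%, and of zero at s = 10%. Power still does not fall below the stated 93% until s exceeds about 10%.

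**5. Disposition percentages.** SAP 6.5.3 names its base (subjects enrolled, in the ID sense) and reports completed and discontinued subjects within the eligible and ineligible groups. On that base, what the 300 counts makes almost no difference. If 300 IDs are issued at s = 10%, completers are 243/300 = 81.0%. If 300 eligible subjects are fitted, 300/0.9 rounds up to 334 consents and completers are 270/334 = 80.8%. At s = 20% the figures are 216/300 and 270/375, both 72.0%. A pooled discontinued percentage that included screen failures would be 0.1(1 − s) + s, which is 19.0% at s = 10%. The rate among eligible subjects can be recovered from the eligible rows: 27/270 = 10.0%.

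**6. Analysis sets.** Protocol 7.8.1 and SAP 6.5.1 define the Full Analysis Set as eligible and dispensed, and the Safety Set as dispensed. Neither uses the word enrolled.

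**The case for a change.** The best case for a change is that the clash rests on the text and needs no assumed rate. Both meanings occur in both documents and no sentence reconciles them. The SAP builds the ID meaning into its disposition summary and into planned Table 14.1.3.3, which lists ineligible subjects under the population of all enrolled subjects, while SAP 6.2 repeats the prohibition. Each site is asked to enrol about 15, so the same ambiguity touches when a site stops. SAP 6.5.3 also reports dispensation status among discontinued subjects, so it can count a non-dispensed person as discontinued. The repair would cost only a few words.

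The textual point stands, and a tidier definition would do no harm. The consequences drawn from it do not stand. The no-replacement chain requires reading a sentence about late-discovered ineligibility as if it covered screening. The tabulation rule in SAP 6.5.3 sets how people are counted in a table; it does not decide who may be replaced. A dispensed-only denominator for discontinuation is a reasonable preference, but the planned rows already let a reader obtain the rate among eligible subjects.

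**Conclusion.** The wording of Protocol 3.3 conflicts with 3.3.1.2 and 5.1.1, and the conflict is a slip in terminology. Followed as written, the plan still gives a sound result. The primary estimate, the exact test and the safety summaries rest on sets defined by dispensing. The stated 93% at n = 270 is correct (93.9% exact). The context supports 300 eligible subjects, and the disposition table states its base and splits its rows by eligibility.

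If the less natural reading were adopted, power would be 93.0% at an assumed 10% screen failure, 89.6% at 20% and 84.7% at 30%, each with an assumed 10% loss among dispensed subjects. Those figures depend wholly on a screen-failure rate that the documents do not give. They take 0.6 as the proportion among analysed answers, and they are before any neutral responses are set aside. No change to the plan is called for.

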### **3.3.1 Eligibility**

#### **3.3.1.1 Inclusion Criteria**

1. Subjects must be age 40 years or older on the date the ICF is signed and have the capacity to provide voluntary informed consent
2. Subjects must be willing and able to comply with all treatment and follow-up/study procedures, as well as willing and able to refrain from using any contact lenses other than those provided for the duration of the study
3. Subjects must be correctable through spherocylindrical refraction to 42 letters (0.1 logMAR) or better (distance, high contrast) in each eye
4. Subjects must have clear central corneas and be free of any anterior segment disorders
5. Subject must wear their current lenses for a minimum of 12 hours per day at least four days per week
6. Subjects must habitually wear a multifocal lens in each eye
7. Subjects must be an adapted multifocal soft contact lens wearer for a minimum of 6 months
8. Subjects must require distance lens correction from +3.00 to -6.00 D in each eye
9. Subjects must be presbyopic and require near add correction from +0.75 to +2.50 D in each eye
10. Subjects must have access to an internet connection to complete an online survey and be able to receive text message

#### **3.3.1.2 Exclusion Criteria**

1. Subjects participating in any drug or device clinical investigation within 30 days prior to entry into this study and/or plan to do so during the period of study participation
2. Subjects who are women of childbearing potential (those who are not surgically sterilized or postmenopausal) are excluded from participation in the investigation if they meet any one of the following conditions:
  - She is currently pregnant

- She plans to become pregnant during the study
- She is breastfeeding

3. Subjects with any systemic disease currently affecting ocular health or that, in the Investigator's opinion, may have an effect on ocular health during the course of the study
4. Subjects with an active ocular disease
5. Subjects who have had any corneal surgery (e.g., refractive surgery)
6. Subjects who have worn gas-permeable (GP) contact lenses within the last 30 days or who have worn polymethylmethacrylate (PMMA) lenses within the last 3 months
7. Subjects who currently wear monovision or toric contact lenses
8. Subjects who are not correctable to 32 letters (0.3 logMAR) with bilateral soft multifocal contact lenses
9. Subjects with an ocular astigmatism >1.00 D in either eye
10. Subjects with anisometropia (spherical equivalent) >2.00 D
11. Subjects with any Grade  $\geq 2$  finding during the slit lamp examination. Subjects with corneal infiltrates of ANY GRADE are not eligible
12. Any "Present" finding during the slit lamp examination that, in the Investigator's opinion, interferes with contact lens wear
13. Any scar or neovascularization within the central 6 mm of the cornea. Subjects with minor peripheral corneal scarring (that does not extend into the central area) that, in the Investigator's opinion, does not interfere with contact lens wear are eligible for this study
14. Subjects who are amblyopic
15. Subjects using any systemic or topical ocular medication that will, in the Investigator's opinion, affect ocular physiology or lens performance
16. Subjects who are allergic to any component in the study care products

If a subject meets all the inclusion criteria and does not exhibit any of the exclusion criteria, the subject is eligible for entry into the study. Ineligible subjects MUST NOT be enrolled in this study. Any subject enrolled in the study who later is found to have not met the eligibility criteria at entry will be discontinued.

